# 10 ADVERSE EVENTS

## 10.1 DEFINITIONS

An **adverse event** (AE) is any untoward medical occurrence in a clinical trial participant, which does not necessarily have a causal relationship with the study intervention.

An **adverse reaction** (AR) is any untoward and unintended response that has occurred due to the intervention

A **serious adverse event** (SAE), **serious adverse reaction** (SAR). Any AE or AR that:

- results in death of the clinical trial participant;
- is life threatening\*;
- requires in-patient hospitalisation^ or prolongation of existing hospitalisation;
- results in persistent or significant disability or incapacity;
- consists of a congenital anomaly or birth defect;
- results in any other significant medical event not meeting the criteria above.

\*Life-threatening in the definition of an SAE or SAR refers to an event where the participant was at risk of death at the time of the event. It does not refer to an event which hypothetically might have caused death if it were more severe.

^Any hospitalisation that was planned prior to enrolment will not meet SAE criteria. Any hospitalisation that is planned post enrolment will meet the SAE criteria.

**Adverse Device Effect (ADE)** is an adverse event related to the use of a medical device. This includes any adverse event resulting from insufficiencies or inadequacies in the instructions for use, the deployment, the implantation, the installation, the operation, or any malfunction of the investigational medical device. An ADE includes any event that is a result of a use error or intentional misuse. Use error refers to an act or omission of an act that results in a different device response than intended by the manufacturer or expected by the user. An unexpected physiological response of the subject does not in itself constitute a use error.

**Serious Adverse Device Effect (SADE)** is an adverse event effect that has resulted in any of the consequences characteristics of a SAE (as defined above). This includes device deficiencies that might have led to a SAE if:

- Suitable action had not been taken
- Intervention had not been made
- If circumstances had been less fortunate

**Anticipated Serious Adverse Device Effect (ASADE)** is a serious adverse device effect..

**Unanticipated Serious Adverse Device Effect (USADE)** is a serious adverse device effect which by its nature, incidence, severity or outcome is not expected in terms of what is known about the device.

We will reference the manufacturer manuals for each device to identify anticipated and unanticipated adverse device effects. The manual for the Dexcom G6 can be found here: <https://s3-us-west-2.amazonaws.com/dexcompdf/G6-CGM-Users-Guide.pdf> and the manual for the tandem t:slim X2 with Control IQ can be found here: [https://www.tandemdiabetes.com/docs/default-source/product-documents/t-slim-x2-insulin-pump/k%c3%a4ytt%c3%b6pas-\(t-slim-x2--pumppu-control-iq-teknologialla\)cf14759775426a79a519ff1100a9fd393f6fb39775426a79a519ff1200a9fd39.pdf?sfvrsn=18a507d7\\_66](https://www.tandemdiabetes.com/docs/default-source/product-documents/t-slim-x2-insulin-pump/k%c3%a4ytt%c3%b6pas-(t-slim-x2--pumppu-control-iq-teknologialla)cf14759775426a79a519ff1100a9fd393f6fb39775426a79a519ff1200a9fd39.pdf?sfvrsn=18a507d7_66).

**Device Deficiency** is an inadequacy of a medical device with respect to its identity, quality, durability, reliability, safety or performance. Device deficiencies include malfunctions, use errors and inadequate labelling.

## 10.2 IDENTIFYING AEs AND SAEs

Participants will be asked about the occurrence of AEs/SAEs at every visit during the study. Open-ended and non-leading verbal questioning of the participant will be used to enquire about AE/SAE occurrence. Participants will also be asked if they have been admitted to hospital, had any accidents, used any new medicines or changed concomitant medication regimens. If there is any doubt as to whether a clinical observation is an AE, the event will be recorded.

AEs and SAEs may also be identified via information from support departments e.g. laboratories.

## 10.3 RECORDING AEs, SAEs and SADEs

When an AE/SAE occurs, it is the responsibility of the Investigator, or another suitably qualified physician in the research team who is delegated to record and report AEs/SAEs, to review all documentation (e.g. hospital notes, laboratory and diagnostic reports) related to the event. The investigator will record all relevant information in the CRF/AE logs.

Information to be collected includes dose, type of event, onset date, Investigator assessment of severity and causality, date of resolution as well as treatment required, investigations needed and outcome.

### 10.3.1 Pre-existing Medical Conditions

Pre-existing medical conditions (i.e. existed prior to informed consent) should be recorded as medical history and only recorded as adverse events if medically judged to have worsened during the study.

### 10.3.2 Worsening of the Underlying Condition during the Trial

Medical occurrences or symptoms of deterioration that are expected due to the participant's underlying condition should be recorded in the patient's medical notes and only be recorded as AEs on the AE log if medically judged to have unexpectedly worsened during the study. Events that are consistent with the expected progression of the underlying disease should not be recorded as AEs.

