#### 2.1.2 Secondary Objectives

- Has the quality of life (QoL) improved with improved blood sugar control?
- Are there fewer hypoglycaemic episodes?
- Is there a lower burden of diabetes care?
- Has the fear of Hypoglycaemia changed as a result of using this technology?
- Has satisfaction with their diabetes treatment improved as a result of using this technology?
- Is there an improvement in HbA1c using this technology?
- Endogenous glucose production and glycerol kinetics as measured by stable isotope studies (glycerol isotope will be used when supply is available)
- Is there a similar improvement in TIR between participants using the HCL system and following a LCD and those using the HCL system and following their pre-study diet

- Is there a difference in QoL between participants using the HCL system and following a LCD and those using the HCL system and following their pre-study diet

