Whilst on an insulin pump the participant will change their own insertion site every three days. This is routine in insulin pump use and is a marked reduction in injections when compared with insulin pens and needles, which is often done five to six times daily. They will also receive advice from the study team with respect to the low carbohydrate diet plans and management of insulin doses for their carbohydrate portions. This advice will be informed by the food diary completed by the participant. Participants in this group will be given blood ketone testing sticks and asked to do these tests daily. If blood ketones are greater than 1.5 mmol/L they will be asked to contact the health care professionals involved in the study or the out of hours care team. Participants will be given a paper record for them to record their ketone readings. This will change from protocol version 8 (28/09/22), from this point routine ketone monitoring will no longer be required. Participants will only be asked to monitor ketones as per standard diabetes management guidelines.

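### The AE-log rule in section 10.3.2 can keep externally assisted hypoglycaemia and diabetic ketoacidosis off the safety record, and no other planned route counts them

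*Combined protocol and SAP*

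**What the plan says.** Section 10.3.2 covers worsening of the underlying condition. Occurrences or symptoms that are expected because of that condition are written in the medical notes and should "only be recorded as AEs on the AE log if medically judged to have unexpectedly worsened during the study". The section then adds: "Events that are consistent with the expected progression of the underlying disease should not be recorded as AEs".

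Section 10.1 is broader. An AE "is any untoward medical occurrence in a clinical trial participant, which does not necessarily have a causal relationship with the study intervention". The categories above it are built on it: an SAE is "Any AE or AR that" meets a listed seriousness criterion, and an adverse device effect "is an adverse event related to the use of a medical device". Section 10.2 says that AEs are asked about at every visit and adds: "If there is any doubt as to whether a clinical observation is an AE, the event will be recorded".

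Section 10 does not name hypoglycaemia, ketosis or DKA, and lists no disease events that must always be logged. Elsewhere the protocol treats these events as important:

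- Section 4.3 excludes people with DKA, or with severe hypoglycaemia requiring external assistance, in the preceding 6 months.
- Section 1.1 (Low Carbohydrate Diet) gives daily ketone testing as the safety measure for the diet arm.
- Section 2.1.2 asks "Are there fewer hypoglycaemic episodes" as a secondary objective.

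**The concern.** Low glucose and ketoacidosis are events that an investigator can reasonably call expected in C-peptide-negative type 1 diabetes. They are also events that an insulin-delivery algorithm and a low-carbohydrate diet could make more or less frequent. A rule that diverts expected disease events from the log therefore acts on the safety outcomes that a reader of this trial will want to see by group.

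The choice is left to judgement in a trial where staff and participants know the allocation. Under section 6.1 (Monitoring Period), staff review Group 2 glucose data daily and pump data at least weekly, and telephone when needed. Group 1 continues standard care. Events may therefore come to notice, and be judged, differently in the two groups. From protocol version 8, new participants also enter Group 1 without randomisation, which makes a uniform recording rule more important.

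**Working it through.** No figure in the plan needs reproducing. The check is mainly of the text.

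**1. Does the rule reach these events?** The sentence about expected progression is the weaker basis, since an acute event need not be progression. The sentence before it is wider: it covers medical occurrences expected from the condition and logs them only if unexpectedly worse. An assisted hypoglycaemic episode or a DKA can fit that description.

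**2. Do other routes catch what the rule removes?**

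| Route | Section | Closes the gap? |
|---|---|---|
| SAE and adverse device effect | 10.1, 10.5 | Not reliably. Both are subsets of AE, so an event ruled not to be an AE can miss both. |
| Device deficiency | 10.1, 10.6 | Partly. It is not defined through AE, so a pump fault or use error is reportable, but events without one, and most Group 1 events, are not covered. |
| Record if in doubt | 10.2 | Only where there is doubt. It does not override the specific rule. |
| Medical notes and health records | 10.3.2, 7.1 | They hold the information, but no extraction or count is described. |
| Endpoints and analyses | 2.2.2, 9.2 | No count of hypoglycaemia or DKA, and no safety analysis. |
| Study CGM | 6.1 | No; see step 3. |

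**3. CGM coverage in Group 1.** Inputs: two blinded periods of 20 days in the 8-month phase (Synopsis, Phase 3), and an aim of at least 14 days of data per period (6.1).

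- Follow-up: 8 × 365.25 / 12 = 243.5 days.
- Worn: 2 × 20 = 40 days; 40 / 243.5 = 16.4%.
- If only the 14-day aim is met: 2 × 14 = 28 days; 28 / 243.5 = 11.5%.

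Group 2 wear is planned to be continuous. In either group, glucose traces show neither whether another person had to help nor whether ketoacidosis occurred. Libre use may continue in Group 1 (4.2), but Libre data are not a listed source (7.1).

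**4. Why a few events matter.** Group 2 had 11 participants at the version 8 amendment (6.1, Randomisation). With no recorded events among n participants, the exact one-sided 95% upper limit on the risk per participant is 1 − 0.05^(1/n).

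- n = 11: 1 − 0.05^(1/11) = 23.8%.
- n = 12 (half of the planned 24): 1 − 0.05^(1/12) = 22.1%.

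The documents give no event rates. For assumed risks of 5%, 10% and 20%, the chance of at least one affected participant among 11 is 1 − (1 − p)^11 = 43%, 69% and 91%. The expected number affected is 11p = 0.55, 1.1 and 2.2. Leaving one or two events off the log could therefore remove the whole signal.

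**The case against.** The strongest reply is that section 10.3.2 concerns worsening of diabetes as a disease. A low glucose on a study pump, or ketoacidosis on a study diet, is more naturally an effect of treatment. With the broad AE definition, the rule to record when in doubt, and questions at every visit about AEs, hospital admissions and accidents, a careful investigator would probably log these events and report an admission for DKA as an SAE. This stands as a description of likely good practice. It does not settle the text: two investigators could each follow the protocol and log differently.

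Table 1 also gives both groups the same scheduled visits from Visit 5 to Visit 7, so the formal questioning after baseline is equal. That stands too. The difference lies in contact between visits and in the judgement applied.

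A reader might infer that the AE log is the only trial record of hypoglycaemia for the 84% of Group 1 follow-up without study CGM. The documents do not support this: 10.3.2 itself sends events to the medical notes, and 7.1 lists electronic health records as source documents. The 16% measures CGM coverage, not AE capture.

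A reader might also want ketone readings compared between groups. Study Visit 3 provides ketone strips, daily tests and a paper record for Group 2 only, with the instruction: "If blood ketones are greater than 1.5 mmol/L they will be asked to contact the health care professionals involved in the study" or the out-of-hours team. From version 8, routine testing stops. A between-group rate would reflect who was tested.

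**Conclusion.** The concern holds for two event types: hypoglycaemia requiring external assistance, and DKA. A stated rule, and not merely missing detail, can take them off the AE log and with that out of the SAE and device-effect routes, and nothing in the plan counts them by another path. It should be changed.

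The size cannot be given as a number of lost events, because that depends on event rates and investigators' judgement, neither of which the documents give. What can be said is that study CGM covers about 16% of Group 1's 8-month follow-up and cannot identify either event type, and that with 11 participants in Group 2 an empty log would still be compatible with a risk of up to 23.8% even if recording were complete.

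The text does not show that events will be missed or that under-recording will differ by group; it shows that both can happen while the protocol is followed. Nor would mending 10.3.2 answer the secondary objective on hypoglycaemic episodes. That objective has no definition, endpoint or analysis, and most non-serious episodes would still lie outside the amended rule.

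**What to change.** - **Recording.** Add to 10.3.2 that, whatever its expectedness, every hypoglycaemic episode requiring external assistance (the term used in 4.3) and every DKA is entered on the AE log in both groups. State the definition of DKA used for recording.
- **Asking.** Under 10.2, put the same question about these two events to both groups at each visit.
- **Reporting.** Add to 9.2 a table by group with events, participants affected and person-time, with Group 1's extension phase shown separately because the treatment differs. Given the size and the non-randomised Group 1 recruits, it is descriptive.
- **Participants already enrolled.** Complete the log from medical notes and health records: at the amendment, 11 + 3 = 14 participants, plus the 2 who left early where their data may still be used. Do this while identifiers are held (12 to 24 months, section 8.1). Without it, recording would change part-way through the trial.
- **Ketones.** Report readings already recorded in Group 2 descriptively, with no between-group rate. Section 1.1 and the inclusion criterion in 4.2 still describe daily monitoring, while Study Visit 3 ends the routine from version 8; these must be reconciled.

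The cost is a somewhat longer AE log, a retrospective records check, and a protocol amendment through the approvals in 13.1. Only recording and reporting change; clinical management does not.

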## 10.4 ASSESSMENT OF AEs AND SAEs

Each AE must be assessed for seriousness, causality, severity and expectedness by the Principal Investigator or another suitably qualified physician in the research team who has been delegated this role.

Where there are two assessments of causality (e.g. between PI and Chief Investigator (CI)), the causality assessment by the Investigator cannot be downgraded. In the case of a difference of opinion, both assessments are recorded and the 'worst case' assessment is used for reporting purposes.

### 10.4.1 Assessment of Seriousness

The Investigator will make an assessment of seriousness as defined in Section 10.1.

### 10.4.2 Assessment of Causality

The Investigator will make an assessment of whether the AE/SAE is likely to be related to the study intervention or medical device according to the definitions below.

- Unrelated: where an event is not considered to be related to the study intervention or device.
- Possibly Related: The nature of the event, the underlying medical condition, concomitant medication or temporal relationship make it possible that the AE has a causal relationship to the study intervention or device.

### 10.4.3 Assessment of Expectedness

#### 10.4.3.1 IMP

If the AE is judged to be related to the study intervention, the PI will make an assessment of expectedness.

The event may be classed as either:

**Expected:** the type of event is expected in line with the study intervention

**Unexpected:** the type of event was not listed in the protocol or related documents/literature as an expected occurrence.

#### 10.4.3.2 Medical Device

If the AE is judged to be related to the device, the investigator will make an assessment of expected based on knowledge of the reaction and any relevant product information. The event will be classed as either:

**Expected:** the reaction is consistent with the effects of the device that are known.

**Unexpected:** the reaction is not consistent with the effects that are known

The above will be assessed in relation to the manufacturer user guides for each device.

#### 10.4.4 **Assessment of Severity**

The Investigator will make an assessment of severity for each AE and record this on the CRF/AE log or SAE form according to one of the following categories:

**Mild:** an event that is easily tolerated by the participant, causing minimal discomfort and not interfering with every day activities.

**Moderate:** an event that is sufficiently discomforting to interfere with normal everyday activities.

**Severe:** an event that prevents normal everyday activities.

Note: the term 'severe', used to describe the intensity, should not be confused with 'serious' which is a regulatory definition based on participant/event outcome or action criteria. For example, a headache may be severe but not serious, while a minor stroke is serious but may not be severe.

### 10.5 REPORTING OF SAEs and SADEs TO THE SPONSOR

Once the Investigator becomes aware that an SAE/SADE has occurred in a study participant, the information will be reported to the ACCORD Research Governance within 24 hours. If the Investigator does not have all information regarding an SAE, SADE they should not wait for this additional information before notifying ACCORD. The SAE report form (and SADE report form where appropriate) can be updated when the additional information is received. Reports will be complete as far as possible and will be signed and dated by the Investigator.

The SAE form (and SADE report form where appropriate) will be transmitted via email to [[contact]](mailto:[contact]). Only forms in a pdf format will be accepted by ACCORD via email. Where missing information has not been sent to ACCORD after an initial report, ACCORD will contact the Investigator and request the missing information. The Investigator must respond to these requests in a timely manner.

Once an SAE or SADE report is received by ACCORD it will be entered onto the ACCORD PhV database by the Research Governance Coordinator or designee.

All safety reports transmitted to ACCORD (including any follow-up information and correspondence) will be kept by the Investigator in the Trial Master File (TMF).

## 10.6 REPORTING OF DEVICE DEFICIENCIES

Device deficiencies will be documented on the ACCORD Medical Device Deficiency Form and will be reported to the sponsor in accordance with section 10.5 above.

On receipt of device deficiency reports, the Research Governance Coordinator, or designee, will assess the report to ensure the correct assessment has been made. In the case of the event meeting SAE, SADE or USADE criteria, the Research Governance Coordinator, or designee will ensure that all the correct reporting procedures have been followed.

The Research Governance Coordinator, or designee, will complete and return the Cover Sheet and Return Receipt or send an email to confirm receipt of the Device deficiency report within 1 working day. If this email/fax is not received within 1 working day of sending the report to ACCORD, the Investigator must telephone ACCORD on [name] to check that the report has been received by ACCORD

The Investigator is responsible for reporting device deficiencies to the relevant NHS Medical Physics department.

Device deficiency reports emailed or faxed to ACCORD and any follow-up information and correspondence will be kept by the Investigator in the TMF.

## 10.7 MEDICAL DEVICE QUARANTINE

If the event is defined as serious i.e. a SAE or device deficiency that could have led to SADE or USADE the Investigator must quarantine the device as soon as possible e.g. segregating the device from other equipment and labelling as not for use with contact details attached.

Until the Sponsor has been given the opportunity to carry out an investigation, all items (together with relevant packaging materials) should be quarantined. They should not be repaired, or discarded or returned to the manufacturer without agreement from the sponsor.

Investigators should contact the manufacturer to obtain information relating to the procedure for returning the device, where considered appropriate.

The device should be cleaned and decontaminated where appropriate, securely packaged, and clearly labelled, including the manufacturer reference number if needed.

# 11 OVERSIGHT ARRANGEMENTS

## 11.1 INSPECTION OF RECORDS

Investigators and institutions involved in the study will permit trial related monitoring and audits on behalf of the sponsor, REC review, and regulatory inspection(s). In the event of audit or monitoring, the Investigator agrees to allow the representatives of the sponsor direct access to all study records and source documentation. In the event of regulatory inspection, the Investigator agrees to allow inspectors direct access to all study records and source documentation.

## 11.2 STUDY MONITORING AND AUDIT

The ACCORD Sponsor Representative will assess the study to determine if an independent risk assessment is required. If required, the independent risk assessment will be carried out by the ACCORD Quality Assurance Group to determine if an audit should be performed before/during/after the study and, if so, at what frequency.

Risk assessment, if required, will determine if audit by the ACCORD QA group is required. Should audit be required, details will be captured in an audit plan. Audit of Investigator sites, study management activities and study collaborative units, facilities and 3rd parties may be performed.

